## LIST OF ABBREVIATIONS

BBV	Blood Borne Virus
CI	Chief Investigator
CNORIS	Clinical Negligence and Other Risks Scheme
CRF	Case Report Form
DAA	Direct Acting Antivirals
DBS	Dried Blood Spot
DMC	Data Monitoring Committee
DOT	Directly Observed therapy
FBC	Full Blood Count
GCP	Good Clinical Practice
GGT	Gamma-Glutamyl Transpeptidase
GP	General Practitioner
HCV	Hepatitis C Virus
IMB	Information-Motivation-Behavioural
ISF	Investigator Site File
LFT	Liver Function Test
MEMS®	medication event monitoring system
NESI	Needle Exchange Service Initiative
PCR	Polymerase Chain Reaction
Peg IFN	Pegylated Interferon
PHQ-9	The Patient Health Questionnaire
PWID	Person Who Injects Drugs
PT	Prothrombin Time
QC	Quality Control
RSI	Reference Safety Information
RBV	Ribavirin
SmPC	Summary of Product Characteristics
SOP	Standard Operating Procedure
SVR	Sustained Viral Response
SVR12	Sustained Viral Response at 12 weeks
TCTU	Tayside Clinical Trials Unit
TMF	Trial Master File
TMG	Trial Management Group
U&Es	Urea & Electrolytes

## **SUMMARY**

Hepatitis C is a blood borne virus that can seriously damage the liver. An estimated 50,000 Scots have been infected with Hepatitis C virus (HCV). The main driver for spread of HCV infection is intravenous drug use. As HCV is highly infectious by the blood borne route through needle sharing, it can infect the person who injects drugs (PWID) early in their habit.

The outcome of HCV infection varies considerably between individuals. Some (up to 25%) are able to clear the infection spontaneously, whilst the remaining 75% become chronically infected. Within the subpopulation of chronically infected patients, some will develop serious liver disease, including cirrhosis and hepatocellular carcinoma, within a few years.

Around two thirds of people who are infected are unaware of it, and often show no symptoms over a long period of time. While there is presently no vaccination for Hepatitis C, improved treatments with shorter duration are now available. This raises the possibility of using therapy as prevention, turning the epidemic off at source, by targeting active PWID who are the main source of new infections. The modelling work of Martin et al, illustrates the startling possibility and impact of treating drug users to reduce the prevalence of HCV.

The focus of this trial will be to ascertain whether oral treatment regimens are effective in the treatment as prevention scenario in an active PWID population where illicit drug taking and poor adherence may reduce treatment efficacy. We will trial 3 different methods of delivering treatment and determine which is most successful in this population. Additionally we will trial an unlicensed combined treatment against HCV genotype 3 infection of shortened duration since current regimens for this genotype are limited.

We will recruit 135 participants and randomise them to one of three arms: daily, directly observed therapy; fortnightly dispensing of drugs; fortnightly dispensing of drugs with a psychological adherence intervention. Randomisation will be stratified according to HCV genotype. Participants will be treated for 12 weeks and followed up 12 weeks post treatment for the measurement of sustained viral response (SVR). The primary outcome measure will be SVR at 12 weeks post treatment (SVR12), as this measure of cure is the determinant of sufficient compliance and efficacy within the 3 treatment arms. Analysis will be by modified intention to treat of all participants who receive one dose of therapy, to show non-inferiority fortnightly dispensing is easier to deliver than daily dispensing.

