## 5.5 RANDOMISATION

### 5.5.1 Randomisation

After successful screening for eligibility and safety, participants will be randomised to either DOT, fortnightly pick up or fortnightly pick up with psychological intervention.

PWID who are eligible for this trial have unpredictable and chaotic lives. It is therefore possible that an individual will consent to take part, provide baseline information and have blood taken for safety and eligibility checking. If eligible they may be randomised. They may then not be seen at the needle exchange for a number of weeks or even months. It is standard clinical practice that pretreatment bloods are valid for a period of 6 months and therefore we will consider baseline bloods taken for the study to be valid for 6 months unless there is a clinical indication to repeat within that period. Any clinical decision on whether bloods need to be repeated within 6 months will be made by the CI. If a consented participant reappears after a period longer than 6 months has elapsed, a documented verbal check will be made to confirm that the individual continues to consent to taking part in the study. The bloods will be re-taken and eligibility will be based on the results of these new blood tests. The blood tests taken closest to the date of treatment initiation will be considered as the baseline data. The viral genotype will not be retested as NHS lab policy is to redo this test only after 5 years have elapsed. After 6 months the baseline CRF will also be repeated to provide up-to-date pretreatment information. In this case, the information originally collected in the baseline CRF will be filed but will not be entered into the electronic data management system (Openclinica) and will not form part of the analysed dataset. To ensure that the correct, most up-to-date baseline data is entered into Openclinica, baseline data will be entered once each participant has started their treatment.

As this is an un-blinded trial, the nurse, or delegated member of staff, and participant will be aware of which arm they are allocated to. Randomisation to each of the three trial groups will be stratified by genotype so that the proportion of genotype 1 vs genotype 3 infected participants will be the same in each group. The Tayside Clinical Trials Unit (TCTU) GCP-compliant online randomisation system, TRuST, will be used by the specialist nurse or delegated, trained member of staff to perform the randomisation.

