### **6.2 DOSING REGIME**

Following randomisation, participants in the DOT group will be issued with their first dose of medication. Those with genotype 1 infection will be given one Zepatier tablet whilst those with genotype 3 will get one Zepatier tablet and one Sovaldi tablet. Participants in each of the fortnightly dosing regimens will be given two week's supply of medication. No per body weight dose adjustment is required and participants with genotype 1 will be treated for 12 weeks, those with genotype 3 for 8 weeks. 12 weeks following the end of treatment blood will be taken from

participants in order to establish whether they have achieved SVR12. Participants will be asked to consent to being followed up annually for five years to enable us to establish reinfection rates. Participants will be asked to use adequate contraception (see section 11.1).

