### 9.2.3 Statistical analysis

Outcomes Data Analysis plan: Analysis of the trial will follow the principles outlined in the ICH E9 'Statistical Principles for Clinical Trials' and carried out by the UKCRC registered Tayside

Clinical Trials Unit (TCTU). Prior to data lock an agreed Statistical Analysis Plan (SAP) will be finalised covering the pre-specified statistical analysis.

The primary outcome of SVR will be assessed as a binary outcome for subjects and so will utilise logistic regression modelling. The numerator will be the number of subjects achieving SVR and the denominator will be total number of patients randomised to each arm. Additionally results will be expressed as a proportion of the estimated HCV infected subjects in needle exchange. The estimated number of infected patients will be based on national survey data and the empirical rate discovered in the trial (allowing for patients who refuse testing). A test of interaction between contingency and pathway will be carried out and if not significant contingency will be assessed independently. If significant then the effect of contingency will be assessed by each pathway separately. As all patients will have either achieved SVR or not and we will assume that drop-outs / lost to follow-up are failures, there will be no missing data in the primary outcome. Extra- binomial variability or over-dispersion will be examined in the logistic model and if present alternative modelling such as negative binomial models will be considered. This will also be adjusted by therapy and genotype; the two factors are interdependent determining length of therapy.

Secondary binary outcomes will be analysed in the same procedure, initially as intention to treat with all eligible patients as the denominator and then to explore the steps in the pathway by per protocol analysis in particular to analyse on treatment success:

- a) Proportion of HCV tested.
- b) Proportion who start HCV treatment within the duration of the study of those identified with HCV.

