- c) Adherence: to compare the longitudinal evolution of adherence to the prescribed regimen between the conventional pathway and the pharmacy led pathway. For each patient, daily adherence will be defined using a binary variable  $Z_t$  indicating whether yes ( $=1$ ) or no ( $=0$ ) the subject has taken their medication on day  $t$ . This longitudinal binary variable will be directly generated from the patient electronically compiled dosing history. Comparison of binary time series is realized using a logistic regression where dependence among observations from a given patient over time is taken into account. The effect of pathway and contingency management on overall adherence will be tested using the above-described model by testing if either the group coefficient or the interaction between the group and time are significantly different from zero.
- d) Proportion who complete the course of those initiating treatment.

Multiple logistic regression modelling will explore the patient and pathway characteristics that are associated with the secondary outcomes and primary outcome. Patient outcomes considered will be age, gender, deprivation, employment, comorbidity, and the psycho-social variables assessed.

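### The protocol gives two different denominators for the primary SVR12 analysis: everyone who took one dose (Summary) and everyone randomised (section 9.2.3)

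*Protocol*

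**What the plan says.** The Summary names SVR12 as the primary outcome, then states: "Analysis will be by modified intention to treat of all participants who receive one dose of therapy", with non-inferiority of fortnightly dispensing as the aim.

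Section 9.2.3 takes up the same outcome as a binary variable and says "the denominator will be total number of patients randomised to each arm". It adds that "we will assume that drop-outs / lost to follow-up are failures, there will be no missing data in the primary outcome". Later in that section a secondary outcome has a different base: "Proportion who complete the course of those initiating treatment".

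Four other places bear on the point:

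- Section 5.5.1 says of participants after randomisation: "They may then not be seen at the needle exchange for a number of weeks or even months". For consented people who return after more than 6 months: "The bloods will be re-taken and eligibility will be based on the results of these new blood tests".
- Section 6.2 says "Following randomisation, participants in the DOT group will be issued with their first dose of medication", and both visit matrices in Appendix 2 show drug administration at the randomisation visit.
- Section 9.1 assumes 95% SVR under DOT, a 14% margin, a 5% level and 90% power. This gives 42 per group, raised to 45 as an allowance for drop-outs.
- On timing, section 9.2.3 says "Prior to data lock an agreed Statistical Analysis Plan (SAP) will be finalised".

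**The concern.** The protocol fixes the primary analysis population twice, in different ways. This is not a detail left for the SAP: any SAP must depart from one of the two statements. Nor does the word for randomised in section 9.2.3 read as loose shorthand for treated, since the same section names treatment initiators separately.

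The population sets the denominator for the non-inferiority verdict. With 45 per arm, each never-dosed person counted as a failure moves that arm's rate by about 2 points (1/45 = 2.2%) against a 14-point margin. In an un-blinded trial whose SAP need only precede data lock, the choice could be made with results by arm already visible.

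There is a related point in section 9.1, which applies whichever population is chosen. Raising 42 to 45 for drop-outs treats them as leaving the denominator, whereas sections 9.2.3 and 9.3 keep them in as failures. Under the one-dose rule, only never-dosed people would leave.

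**Working it through.** **The plan's own figure.** Inputs from section 9.1: 95% SVR under DOT, margin 0.14, 5% level, 90% power. Equal SVR in the fortnightly arm is assumed.

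n = (1.645 + 1.282)² × 2 × 0.95 × 0.05 / 0.14² = 41.5, so 42 per arm.

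This matches the protocol if the 5% is one-sided. One-sided 2.5% would need 51 per arm. The calculations below therefore use one-sided 5%. The step to 45 implies a loss of 3/45 = 6.7%.

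**Can the two sets differ?** Section 6.2 and the matrices suggest that most people are dosed at the randomisation visit. Section 5.5.1 nevertheless describes people randomised and then absent for long periods, with eligibility rechecked on new bloods after 6 months. That section also delays entry of baseline data until treatment has started, so it treats starting as a separate event. Sections 4.1 and 9.3 say how drop-outs are handled, not who belongs to the analysis set.

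**One example.** Assume 45 randomised per arm, with 2 never dosed in the fortnightly arm and 0 in DOT. Lower bound = d − z × √[p₁(1−p₁)/n₁ + p₂(1−p₂)/n₂], where d is fortnightly minus DOT.

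| Population | Fortnightly v DOT | d (points) | Bound, one-sided 5% | Bound, one-sided 2.5% |
|---|---|---|---|---|
| One dose | 40/43 v 43/45 | -2.5 | -2.5 − 1.645 × 4.95 = -10.7 | -12.2 |
| All randomised | 40/45 v 43/45 | -6.7 | -6.7 − 1.645 × 5.60 = -15.9 | -17.6 |

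Against -14, the first rule shows non-inferiority and the second does not, at either level. Newcombe intervals at one-sided 5% also reverse the verdict (-12.2 v -17.1).

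**How often the rules disagree.** Fix the number never dosed, let successes among starters be independent Binomial(45 − k, 0.95) in each arm, enumerate all outcomes and apply the same one-sided 5% bound.

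| Never dosed (fortnightly, DOT) | Trials in which the rules disagree | Rule that alone shows non-inferiority |
|---|---|---|
| 1, 0 | 12.5% | one dose |
| 2, 0 | 32.3% | one dose |
| 0, 1 | 3.9% | all randomised |
| 0, 2 | 7.0% | all randomised |
| 1, 1 | 5.2% | one dose |
| 2, 2 | 10.5% | one dose |

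**Section 9.1.** Power = Φ(0.14/√(2p(1−p)/45) − 1.645), with p the SVR rate after losses are counted as failures.

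| Meaning of the 95% | p | Power |
|---|---|---|
| Already counts losses as failures | 0.95 | 92.0% |
| Excludes losses, 1/45 lost | 0.95 × 44/45 = 0.9289 | 82.6% |
| Excludes losses, 2/45 lost | 0.95 × 43/45 = 0.9078 | 74.2% |
| Excludes losses, 3/45 lost | 0.95 × 42/45 = 0.8867 | 67.4% |

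Exact enumeration of the same test gives 89.9% for the first row and 68.1% for the last.

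**The case against.** The strongest reply is that the contradiction may have little practical effect. The sets differ only by never-dosed people, dosing is scheduled at the randomisation visit, and no non-start rate is given. The 6-month recheck is written for consented participants, so a randomised person becoming ineligible before dosing is an inference. The 32.3% needs two non-starters in one arm and none in the other. With one in each arm the rules agree in about 95% of trials. The planned model is an adjusted logistic regression, not an unadjusted risk difference. All of this is fair. It makes the figures illustrations rather than forecasts, but it does not reconcile the two statements.

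A second reply is that all-randomised is not a neutral choice. Counting non-starters as failures can hide inferiority if more people fail to start under DOT. Suppose 15% v 5% never start and SVR among those dosed is 95% v 81%, exactly at the margin. The all-randomised difference is then 0.8075 − 0.7695 = 3.8 points, and the chance of declaring non-inferiority is about 32% instead of 5%. Section 9.2.3 also contains text that does not fit this trial's arms, such as a pharmacy-led pathway. These points stand as reasons to report both populations. They are not reasons to leave both as primary.

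Third, section 9.1 can be read as an arm-level rate with losses already counted, in which case no power is lost. That reading is possible, so the power point is conditional and separate from the contradiction.

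**Conclusion.** The concern holds and must be fixed. The protocol sets two incompatible denominators for its sole primary outcome, and nothing in it chooses between them. The contradiction rests on the text alone.

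Its size depends on how many people are randomised and never dosed, which the protocol does not state. For one or two such people, in one arm or in each, and 95% SVR among starters, the two rules give opposite verdicts in 3.9% to 32.3% of trials. The risk runs in both directions and is larger when it is fortnightly participants who go undosed. An SAP that is not shown may settle the matter, but the protocol would still carry both rules.

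On section 9.1, power at 45 per arm is about 92% (89.9% by exact enumeration) if the 95% already counts losses. It is about 67% if the 95% excludes them and the implied 3/45 are lost.

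**What to change.** Before outcome data are reviewed by arm, state one primary population in the Summary and in section 9.2.3. All randomised, with never-dosed people counted as failures, is the natural choice for an open-label comparison of delivery routes, since section 1.2 makes uptake of treatment, as well as adherence, something to be demonstrated. It is also what section 9.2.3 already says, so only the Summary need change. Name the one-dose set as a sensitivity analysis and report both results. If the sponsor prefers the one-dose set as primary, reverse the roles and amend section 9.2.3 instead.

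In section 9.1, say whether the 95% already counts losses as failures, and restate the power on that basis rather than enlarge the sample.

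The cost is one sentence in the Summary, one in section 9.1 and one named sensitivity analysis, put through the amendment approvals of section 14.1. No extra participants or visits are needed. The primary comparison needs only arm, genotype and failure status. Because section 5.5.1 enters baseline data only after treatment starts, never-dosed people would be missing from the exploratory covariate models, but not from the primary analysis. The one possible loss is a lower stated power, and only if the 95% excludes losses.

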## **1 INTRODUCTION**

### **1.1 BACKGROUND**

Hepatitis C is a blood borne virus that can seriously damage the liver. An estimated 50,000 Scots have been infected with Hepatitis C virus (HCV). The main driver for spread of HCV infection is intravenous drug use. As HCV is highly infectious by the blood borne route through needle sharing, it can infect the PWID early in their habit. With the advent of more effective therapies of shortening duration, it raises the possibility of using therapy as prevention, turning the epidemic off at source, by targeting active infected drug users who are the main source of new infections.

Current treatment pathways focus on populations drawn from those known to drug problem services and former drug users. Some older periodic drug users are tested for HCV and are offered accelerated access into opiate substitution programs and early antiviral therapy. This treatment activity will reduce the health consequences of HCV infection but will have little impact on the group with active acquisition of HCV and hence the prevalence of HCV will remain the same, as any participants cured with anti-virals are more than replaced with new infections.

The modelling work of Martin et al, raises the startling possibility of the profound impact of treating small numbers of drug users on the prevalence of HCV, the work shows that treating as few as 10-20 per 1000 drug users per year can reduce HCV prevalence by 50-90% over 10 years. This has generated in the HCV field, the concept of treatment as prevention. The scale of the benefit is exponentially related to prevalence of HCV in the population, the lower the prevalence the bigger the impact. The model has some limitations, it groups all drug users together and assumes a similar risk of infection for those on methadone and those actively injecting and assumes a high rate of turn over from methadone back to active injecting and further assumes treatment is only possible during the opiate substitution phase.

To test the feasibility of the model of Martin et al we ran the “Eradicate C” trial. This trial focuses on treating those drug users outside services where the impact on prevalence could be even more impressive, for such a relatively small investment. This group had never been previously targeted for therapy as it was believed to be too difficult to achieve the required adherence to therapy. The aim was to treat 20-40 highly active injecting drug users per year, recruited from Needle Exchange services. This trial showed that it was possible to treat this participant group with interferon based regimens +/- telaprevir, with SVRs that matched the conventional treatment trial outcomes. Adherence is crucial to therapy success and supervised interferon injections make therapy robust and may cover for lesser adherence to the ribavirin and protease inhibitor. The Eradicate C trial demonstrated that it is possible to deliver interferon based therapies to very active drug users and achieve cure rates that will power treatment as prevention.

## 1.2 RATIONALE FOR TRIAL

Oral anti-HCV regimens that are interferon free and have virtually no side-effects are now the standard of care in conventional treatment populations. The medication should be taken daily to optimise therapeutic success, and if adherence is poor in the actively injecting population it is possible that the effectiveness of the new oral drugs will be reduced. It is key to know if all oral directly acting antivirals (DAA) regimens are robust and maintain SVR rates in this population. The real world SVR rate combined with drug cost, re-infection rate and emergence of viral resistance will determine if this treatment as prevention model is cost-effective with DAAAs. Directly observed therapy (DOT) is the ultimate adherence aid, but it is more costly and draconian so that it may discourage participants, especially this group, from taking up therapy. Therefore we need to demonstrate that treatment uptake and adherence is sufficient to maintain the SVR rate at a level which makes treatment as prevention cost effective. We will compare three means of delivery: daily DOT vs fortnightly pick up of therapy vs. fortnightly pick-up of therapy with a psychological intervention for adherence. The DOT method of treatment has not been explored in this difficult to find and engage population previously. Contingency management in the form of protein drinks for successful completion of each fortnight of treatment will be provided in all three arms of the trial. A comparison of the three pathways mentioned above will show which pathway shows best acceptability to participants and greatest compliance

The advent of DAAAs with their reduced side effect profiles, shorter treatment duration and high SVR rates have the potential to reduce the burden of treatment providing high levels of adherence can be maintained. However, the use of DAAAs alone are unlikely to be sufficient to achieve the required levels of adherence. In addition, the use of DAAAs will not address the psychosocial factors known to influence adherence. To maximise participant outcomes, it will therefore be necessary to design interventions to promote adherence. One factor consistently cited as essential to treatment adherence is the provision of educational interventions regarding HCV, treatment of the condition and prognosis. However, these interventions (e.g.4,5,6) have not been shown to be effective in improving treatment adherence. Several possible reasons exist for this discrepancy. First, the studies were generally of low quality with evidence of systematic bias (e.g. non-randomisation) and varied considerably in the structure and content of the intervention delivered. Second, none of the studies described a clear theoretical model of adherence behaviour upon which the interventions were based. Third, all interventions utilised generic education information about HCV. Evidence suggests that individualised and personalised information is essential in the promotion of adherence (e.g.8,9,10). All the factors likely limited the ability of the education to influence adherence in these studies. Finally, none of the studies investigated adherence in PWID or with DAA treatments only and therefore the effectiveness of such interventions in this population with newer treatment approaches is unknown. This trial will therefore investigate the effectiveness of a nurse-led educational intervention for adherence to DAAAs in a PWID population.

Whilst the combination of Grazoprevir and Elbasvir is licensed for treatment of HCV genotype 1, treatment of HCV genotype 3 is more problematic. The C-SWIFT trial has recently shown that the combination of Grazoprevir, Elbasvir and Sofosbuvir is an effective and safe 8 week treatment for HCV genotype 3, resulting in high SVR rates. Whilst all 3 drugs are licensed for treatment of HCV, the combination is not yet licensed. We will use this combination to treat HCV genotype 3 infections in this trial.

Hepatitis C virus is prone to develop resistance to DAAs since it has a high replication rate and therefore forms large numbers of genetically-distinct viral variants. We will investigate whether participants who do not achieve SVR are infected with a drug resistant strain of HCV by sequencing the NS3 and NS5A regions of virus present within their blood. The proteins of these genes are targeted by the DAA medications and if their structure is altered the DAA may no longer be effective.

The trial will also explore whether the taking of illicit drugs affects the efficacy of treatment. While the main effect is likely to be via adherence, it is also possible that some of the illicit drugs may interact with the DAAs. A log of illicit drugs used by the participants will be kept and used to identify any candidate interactions for further investigation.

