## **9 STATISTICS AND DATA ANALYSIS**

### **9.1 SAMPLE SIZE CALCULATION**

Statistical analysis will be conducted in compliance with TASC SOPS.

We propose to conduct this project as a randomised trial to show that DAA therapy in very active PWIDs administered fortnightly with or without adherence intervention is non-inferior to DOT. We will compare pathways sequentially comparing DOT vs fortnightly delivery and then DOT versus fortnightly pickup with adherence intervention. Fortnightly pick up will be more cost effective than the other two options so long as adherence and efficacy matches that of the DOT and fortnightly plus adherence intervention. If we assume a 95% SVR rate (based on published studies) in the DOT arm of the trial in this population and a non-inferiority limit of 14% (which would be likely to maintain cost-effectiveness) then at a 5% significance level and 90% power

we would need a sample size of 42 in each group 126 in total. To allow for drop-outs we will aim to recruit 135 individuals, 45 per group.

A Statistical Analysis Plan (SAP) will be prepared for analysis of primary and secondary outcomes and will include a plan for handling missing data

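### The contrast that isolates the adherence intervention, fortnightly pick-up with it versus without it, is not named, and the adherence model in 9.2.3(c) compares pathways that are not arms of this trial

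*Protocol*

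**What the plan says.** - **Aim.** Section 1.2 criticises earlier education studies for non-randomised designs, lack of theory and generic content, and concludes: "This trial will therefore investigate the effectiveness of a nurse-led educational intervention for adherence to DAAAs in a PWID population". The Summary adds that the trial will try three delivery methods and "determine which is most successful in this population".
- **Design.** Under section 3.1, arms 2 and 3 both collect medication fortnightly. Arm 3 also has the nurse-led interview and personalised booklet. Arms 1 and 2 get the standard information booklet.
- **Named pairs.** Section 9.1 sets out to show that therapy "administered fortnightly with or without adherence intervention is non-inferior to DOT" and gives the order: "We will compare pathways sequentially comparing DOT vs fortnightly delivery and then DOT versus fortnightly pickup with adherence intervention". It also says that plain fortnightly pick-up will be the more cost-effective option provided that it matches both DOT and the intervention arm.
- **Three-arm statements.** Section 1.2, Table 1 and 9.2.1 compare the three arms in general terms. Section 9.2.2 compares adherence across the three, using a daily log for DOT and pill counts and MEMS caps for the fortnightly arms. None of them names a pair.
- **Adherence model.** Section 9.2.3(c) models daily adherence from an electronic dosing history and sets the comparison "between the conventional pathway and the pharmacy led pathway".

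**The concern.** The effect of the intervention is the difference between arms 3 and 2, where dispensing is the same and only the intervention differs. DOT versus arm 3 changes dispensing and intervention together, so it cannot separate them. Both fortnightly arms could be non-inferior to DOT with no intervention effect at all. If one passed and the other failed, that would not be evidence of a difference between them.

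The protocol also gets the wording of its one detailed adherence model wrong: the groups it names do not exist here. An analyst could not run it as written, and a SAP that followed it would carry the mismatch forward. At stake are the stated aim on the intervention and half of the cost-effectiveness premise in 9.1. If the contrast is not fixed in advance, the pair, outcome and instrument could be chosen after the data are seen.

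**Working it through.** **1. What the sample size was built on.** Inputs from 9.1: "If we assume a 95% SVR rate (based on published studies) in the DOT arm", "a non-inferiority limit of 14" percentage points, 5% significance, 90% power. Assuming 95% in the fortnightly arm too, which 9.1 does not state:

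n per arm = (z₁₋α + z₀.₉₀)² × 2p(1−p) / margin²

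- One-sided 5%: (1.645 + 1.282)² × 2 × 0.95 × 0.05 / 0.14² = 41.5, so 42 per arm and 126 in all. This is the protocol's figure.
- One-sided 2.5%: 50.9, so 51 per arm, which does not match.

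The 42 is therefore the size for one fortnightly arm against DOT. Recruiting 45 allows 3/45 = 6.7% for drop-out. No part of it refers to arm 3 versus arm 2.

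**2. Why two comparisons with DOT do not answer the question.** This is an illustration, not a forecast. DOT at its assumed rate gives 0.95 × 45 = 42.75, taken as 43 of 45. The upper one-sided 95% limit for DOT minus a fortnightly arm is the difference + 1.645 × SE, where SE = √[p₁(1−p₁)/45 + p₂(1−p₂)/45].

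| Fortnightly arm | Difference | SE | Upper limit | Within 14 points? |
|---|---|---|---|---|
| 41/45 | 4.4 | 5.24 | 13.1 | yes |
| 40/45 | 6.7 | 5.60 | 15.9 | no |

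If arm 3 had 41 responders and arm 2 had 40, one would pass and the other fail. The direct difference would be 1/45 = 2.2 points with SE 6.32, so a 95% CI of 2.2 ± 1.96 × 6.32, from −10.2 to +14.6. That gives no support for an intervention effect.

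**3. Precision of the direct SVR12 contrast.** Half-width = 1.96 × √[p₂(1−p₂)/45 + p₃(1−p₃)/45]. The intervention arm is assumed at 95%. The rates for plain fortnightly are also assumptions, the lowest being 95 − 14 = 81%.

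| Plain fortnightly | Calculation | Half-width |
|---|---|---|
| 95% | 1.96 × √(0.001056 + 0.001056) | 9.0 points |
| 88% | 1.96 × √(0.002347 + 0.001056) | 11.4 points |
| 81% | 1.96 × √(0.003420 + 0.001056) | 13.1 points |

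These are Wald intervals. At 95% only 45 × 0.05 = 2.25 failures are expected per arm, so they indicate scale only.

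**4. Power of the same contrast** (two-sided 5%, 45 per arm, intervention arm at 95%). Power = Φ{[Δ − 1.96√(2p̄(1−p̄)/45)] / √[p₂(1−p₂)/45 + p₃(1−p₃)/45]}, with p̄ the mean of the two rates. For 81%: (0.14 − 1.96 × 0.0685) / 0.0669 = 0.086, giving 53%. For 85% it is 35%, and for 90% it is 14%. Fisher's exact test gives 43%, 23% and 6%.

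**5. Which data 9.2.3(c) can use.** Sections 3.1, 5.5.2 and 6.1.4 put the electronic caps on the Sovaldi bottles. Only genotype 3 participants receive Sovaldi, and only the fortnightly arms are given bottles. Section 9.2.2 likewise takes cap data from the two fortnightly groups. DOT has a daily log. Genotype 1 participants in the fortnightly arms have pill counts per fortnight, which give no daily series. Arms 2 and 3 are thus the only pair measured with the same instruments, and only their genotype 3 participants have the electronic history that the model needs.

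**The case against.** A reader might infer that the protocol compares the fortnightly arms only with DOT and that intervention versus no intervention is never analysed. The documents do not support that. Section 1.2, Table 1 and 9.2.1 compare all three arms, 9.2.2 plans an adherence comparison across them, and a three-level arm factor in the logistic model of 9.2.3 would produce the contrast. Section 9.1 states the SVR hypotheses that size the trial and does not claim to list every comparison. The aim in 1.2 is about adherence and stands in rationale text, while Tables 1 and 2 contain no separate objective for the intervention. Pairwise contrasts are often left to the SAP, which is not shown and may name this one.

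All of that stands against the strong reading. It does not remove the narrower point. Where the protocol does name pairs, they serve a different question from the aim in 1.2, and 9.1 itself relies on plain fortnightly matching the intervention arm. The groups in 9.2.3(c) are a misstatement in the current text, not a detail left for later.

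It is also fair that simply putting arm 3 versus arm 2 in place of the pathways in 9.2.3(c) would drop DOT from that model and overlook the missing electronic data for genotype 1. The fix has to respect both.

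**Conclusion.** The concern holds in this form: the protocol states an aim to investigate the intervention's effectiveness for adherence, but the contrast that isolates it is not named, not tied to a hypothesis and not sized. The one detailed adherence model names groups that are not arms. The general three-arm comparisons could supply the contrast without specifying it, and on adherence they measure DOT with a different instrument from the other two arms.

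The direct SVR12 difference would be known to within about 9 to 13 points, if 45 per arm are analysed and the assumed rates hold. For adherence, the outcome in the stated aim, no precision can be given because the documents contain no SD. The one-sided 5% level is inferred from the match with 42 per group. The non-inferiority comparisons with DOT are unaffected, so this is a change that should be made rather than a flaw in the primary analysis.

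**What to change.** 1. In 9.2.3(c), replace the two pathways by the three trial arms. State that in the fortnightly arms the electronic daily series exists only for genotype 3 participants (MEMS caps).
2. In 9.2.2 and 9.2.3, name fortnightly plus intervention versus fortnightly alone as the contrast for the aim in 1.2. Report:
   - the adherence difference by pill count in all participants of these two arms, and by MEMS caps in genotype 3;
   - the SVR12 risk difference.

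   Give each with a 95% CI and adjust for genotype. For SVR12, use an interval method suited to few failures. Label these as secondary estimates without a power claim.
3. Keep the three-arm adherence comparison in 9.2.2.
4. Reword the Summary's promise to "determine which is most successful in this population" so that it matches what the comparisons can show.

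The cost is protocol and SAP wording and one more contrast on data already collected, with no change to arms, visits or sample size. The downside is that the added contrast has low power, so a wide interval must not be read as showing that the intervention has no effect.
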